Table 6-6	Guidelines for the management of hepatitis C flare	32
Table 6-7	Clinically relevant drug interactions: inducers, and inhibitors of isoenzyme CYP3A	34
Table 6-8	Clinically relevant drug interactions: substrates, inducers, inhibitors of PgP and PgP/CYP3A dual inhibitors	36
Table 7-1	Visit evaluation schedule	37

List of abbreviations

4E-BP1	4E-binding protein
AE	Adverse event
ALT	Alanine aminotransferase/glutamic pyruvic transaminase/GPT
ANC	Absolute neutrophil count
AST	Aspartate aminotransferase/glutamic oxaloacetic transaminase/GOT
AUC	Area under the curve
BAL	Bronchoalveolar lavage
BCG	Bacillus Calmette-Guérin
CDS	Core data sheet
CoA	Coenzyme A
CPK	Creatine phosphokinase
CRF	Case Report Form
CT	Computer tomography
CTCAE	Common terminology criteria for adverse events
CYP3A4	Cytochrome P450 3A4
DDI	Drug-drug interaction
DLCO	Diffusing capacity of the Lung for Carbon Monoxide
DNA	Deoxyribonucleic acid
DS&E	Drug Safety and Epidemiology
EOT	End of treatment
EU	European Union
FDA	Food and drug administration
GERD	Gastroesophageal reflux disease
HbA1c	Hemoglobin A1c
HBcAb	Hepatitis B core antibody
HbsAb	Hepatitis B surface antibody
HbsAg	Hepatitis B surface antigen
HBV	Hepatitis B virus
HCV	Hepatitis C virus
HMG	3-hydroxy-3-methyl-glutaryl
IB	Investigator brochure
INR	International Normalized Ratio
IRB	Institutional Review Board
IUD	Intrauterine device
IUS	Intrauterine system
IV	Intravenous
log ₁₀	Decadic logarithm (common logarithm)
MRI	Magnetic resonance imaging
mTOR	Mammalian target of rapamycin
NCI	National Cancer Institute
PCR	Polymerase chain reaction
PgP	P-glycoprotein
PFT	Pulmonary function tests

PI3K	Phosphoinositide 3-kinase
PNET	Pancreatic neuroendocrine tumor
RCC	Renal cell carcinoma
RMP	Risk management plan
RNA	Ribonucleic acid
SAE	Serious Adverse Event
SEGA	Subependymal giant cell astrocytoma
TS	Tuberous sclerosis
ULN	Upper limit of normal
US	United States
VEGF	Vascular endothelial growth factor
WOCBP	Women of child-bearing potential

Glossary of terms

Assessment	A procedure used to generate data required by the study
Baseline	For efficacy evaluations, the baseline assessment will be the last available assessment before or on the date of randomization. For safety evaluations (i.e. laboratory assessments and vital signs), the baseline assessment will be the last available assessment before or on the start date of study treatment. The value obtained at baseline assessments, referred to as “baseline value” will be used as reference for the patient.
Control drug	A study treatment used as a comparator to reduce assessment bias, preserve blinding of investigational drug, assess internal study validity, and/or evaluate comparative effects of the investigational drug
Dose level	The dose of drug given to the patient (total daily or weekly etc.)
Enrollment	Point/time of patient entry into the study; the point at which informed consent must be obtained (i.e. prior to starting any of the procedures described in the protocol)
Investigational drug	The study treatment whose properties are being tested in the study; this definition is consistent with US CFR 21 Section 312.3 and is synonymous with “investigational new drug.”
Investigational treatment	Drug whose properties are being tested in the study as well as their associated placebo and active treatment controls (when applicable). This also includes approved drugs used outside of their indication/approved dosage, or that are tested in a fixed combination. Investigational treatment generally does not include other study treatments administered as concomitant background therapy required or allowed by the protocol when used in within approved indication/dosage
Medication number	A unique identifier on the label of each study treatment package which is linked to one of the treatment groups of a study
Other study treatment	Any drug administered to the patient as part of the required study procedures that was not included in the investigational treatment
Patient	A unique identifying number assigned to each patient/subject/healthy volunteer who enrolls in the study
Period	A subdivision of the study timeline; divides stages into smaller functional segments such as screening, baseline, titration, washout, etc.

Premature patient withdrawal	Point/time when the patient exits from the study prior to the planned completion of all study treatment administration and/or assessments; at this time all study treatment administration is discontinued and no further assessments are planned, unless the patient will be followed for progression and/or survival
Stop study participation	Point/time at which the patient came in for a final evaluation visit or when study treatment was discontinued whichever is later
Study treatment	
Includes any drug or combination of drugs in any study arm administered to the patient (subject) as part of the required study procedures, including placebo and active drug run-ins.
 
In specific examples, it is important to judge investigational treatment component relationship relative to a study treatment combination; study treatment in this case refers to the investigational and non-investigational treatments in combination.

Study treatment discontinuation	Point/time when patient permanently stops taking study treatment for any reason; may or may not also be the point/time of premature patient withdrawal
Supportive treatment	Refers to any treatment required by the exposure to a study treatment, e.g. premedication of vitamin supplementation and corticosteroid for pemetrexed disodium.
Variable	Identifier used in the data analysis; derived directly or indirectly from data collected using specified assessments at specified time points

Schema

Step 1¹

R
E
G
I
S
T
E
R

RT or chemoRT
administration

Step 2²

R
E
G
I
S
T
E
R

Everolimus
Administration³

↓↓↓↓

CORRELATIVE STUDIES⁴

¹ Patients with locally advanced squamous cell carcinoma of the Head and Neck treated with curative intent either in the post-operative or definitive setting with high dose radiotherapy (RT ≥ 50 Gy) with or without chemotherapy (chemoRT) will be eligible

² Verify eligibility for everolimus treatment. Patients with clinically severe gland dysfunction (i.e., those with loss of at least 50% of the pre-radiotherapy value) will be eligible for everolimus treatment.

³ Everolimus (5 or 10 mg) po qd, x 5days only, starting 2 weeks after definitive treatment completion

⁴ Saliva flow rates and xerostomia surveys will be obtained at baseline, after 3 and 6 weeks of RT/chemoRT, prior to everolimus administration, at completion of the 5 day everolimus course and at 1,3 and 6 months after RT/chemoRT completion

1 Background

1.1 Overview of disease pathogenesis, epidemiology and current treatment

The clinical symptom of xerostomia (dry mouth syndrome) has been reported as a principle side effect of chronic prescription drug use particularly in the elderly, chemotherapy, therapeutic radiation of the head and neck region, and systemic autoimmune diseases such as Sjögren's syndrome. Approximately 500,000 new patients are diagnosed annually with head and neck cancer worldwide. It is estimated that the tolerance dose for 50% complications rate (TD50) for the parotid gland is 28.4 Gy and the submandibular glands is 39 Gy with the daily dose exposure of <2Gy/day. Regrettably, many surviving patients that received radiotherapy suffer from chronic consequences of oral complications including hyposalivation, increased dental caries, reduced taste and smell, increased risk for oral infections, hampered speech, and malnutrition. Regardless of causal etiology, xerostomia has a significant negative impact on quality of life and presents an elevated financial burden to these individuals.

1.2 Introduction to investigational treatment(s) and other study treatment(s)

Everolimus is a novel derivative of rapamycin. It has been in clinical development since 1996 as an immunosuppressant in solid organ transplantation. Everolimus is approved in Europe and other global markets (trade name: Certican®) for cardiac and renal transplantation, and in the United States (trade name: Zortress®) for the prevention of organ rejection of kidney transplantation.

Afinitor® was approved for adults with advanced renal cell carcinoma (RCC) after failure of treatment with sunitinib or sorafenib in 2009. In 2010, Afinitor® received United States (US) approval for patients with subependymal giant cell astrocytoma (SEGA) associated with tuberous sclerosis complex (TSC). Everolimus is also available as Votubia® in the European Union (EU) for patients with SEGA associated with TSC who require therapeutic intervention but are not candidates for curative surgical resection. Afinitor® was approved for “progressive pancreatic neuroendocrine tumor (PNET) in patients with unresectable, locally advanced, or metastatic disease” in 2011 in various countries, including the US and Europe. In 2012 Afinitor® received approval for the treatment of postmenopausal women with advanced hormone receptor-positive, HER2- negative breast cancer (advanced HR+ BC) in combination with exemestane, after failure of treatment with letrozole or anastrozole. Furthermore in 2012, Afinitor® received approval for the treatment of patients with TSC who have renal angiomyolipoma not requiring immediate surgery. In the US, Afinitor® was approved in 2016 for advanced non-functional NET of gastrointestinal (GI) or lung origin.

Approximately 44,060 cancer patients (excluding those patients who received marketed Afinitor®, those on planned and roll over studies as well as excluding investigator-sponsored studies) have been treated with everolimus as of 31-Mar-2016:

- 25,356 patients in Novartis-sponsored clinical trials
- 2,043 patients in the individual patient supply program

The following is a brief summary of the main characteristics of Everolimus. More complete information can be obtained from the Everolimus Investigator's Brochure (IB).

1.2.1 Overview of Everolimus

[figure not shown]
Everolimus is a derivative of rapamycin which acts as a signal transduction inhibitor (Table 1-1, Figure 1-1). Everolimus selectively inhibits mTOR (mammalian target of rapamycin), specifically targeting the mTOR-raptor signal transduction complex. mTOR is a key serine-threonine kinase in the PI3K/AKT signaling cascade, which is known to be dysregulated in a wide spectrum of human cancers (Boulay and Lane 2007).

Everolimus is being investigated as an anticancer agent based on its potential to act

- directly on the tumor cells by inhibiting tumor cell growth and proliferation;
- indirectly by inhibiting angiogenesis leading to reduced tumor vascularity (via potent inhibition of tumor cell VEGF (vascular endothelial growth factor) production and VEGF-induced proliferation of endothelial cells).

Table 1-1 Everolimus - Drug substance

Chemical name	(1R,9S,12S,15R,16E,18R,19R,21R,23S,24E,26E,28E,30S,32S,35R)-1,18-dihydroxy-12-[(1R)-2-[(1S,3R,4R)-4-(2-hydroxyethoxy)-3-methoxycyclohexyl]-1-methylethyl]-19,30-dimethoxy-15,17,21,23,29,35-hexamethyl-11,36-dioxa-4-aza-tricyclo[30.3.1.0 ^{4,9}]hexatriaconta-16,24, 26,28-tetraene-2,3,10,14,20-pentaone
International non-proprietary name	Everolimus

Figure 1-1 Chemical structure of Everolimus

1.2.1.1 mTOR pathway and cancer

At the cellular and molecular level, Everolimus acts as a signal transduction inhibitor. It selectively inhibits mTOR (mammalian target of rapamycin), a key protein kinase which regulates cell growth, proliferation and survival. The mTOR kinase is mainly activated via the phosphatidylinositol 3-kinase (PI3-Kinase) pathway through AKT/PKB and the tuberous sclerosis complex (TSC1/2). Mutations in these components or in PTEN, a negative regulator of PI3-kinase, may result in their dysregulation. Abnormal functioning of various components

of the signaling pathways contributes to the pathophysiology of numerous human cancers. Various preclinical models have confirmed the role of this pathway in tumor development (Cohen et al 2005).

The main known functions of mTOR include the following (Bjornsti and Houghton 2004):

- mTOR functions as a sensor of mitogens, growth factors and energy and nutrient levels;
- Facilitating cell-cycle progression from G1-S phase in appropriate growth conditions;
- The PI3K/mTOR pathway itself is frequently dysregulated in many human cancers, and oncogenic transformation may sensitize tumor cells to mTOR inhibitors;
- PI3-kinase mutations have been reported in the primary tumor in 10-20% of human colorectal cancers (Frattini 2005, Velho 2005);
- The loss of PTEN protein, either through gene deletion or functional silencing (promoter hypermethylation), is reported in approximately 60% of primary human colorectal cancers (Goel et al 2004);
- The mTOR pathway is involved in the production of pro-angiogenic factors (i.e., VEGF) and inhibition of endothelial cell growth and proliferation;
- Through inactivating eukaryotic initiation factor 4E binding proteins and activating the 40S ribosomal S6 kinases (i.e., p70S6K1), mTOR regulates protein translation, including the HIF-1 proteins. Inhibition of mTOR is expected to lead to decreased expression of

HIF-1.

1.2.1.2 Non-clinical experience

Everolimus inhibits the proliferation of a range of human tumor cell lines *in vitro* including lines originating from lung, breast, prostate, colon, melanoma and glioblastoma. IC50s range from sub/low nM to μ M. Everolimus also inhibits the proliferation of human umbilical vein endothelial cells (HUVECS) *in vitro*, with particular potency against VEGF-induced proliferation suggesting that Everolimus may also act as an anti-angiogenic agent. The anti-angiogenic activity of Everolimus was confirmed *in vivo*. Everolimus selectively inhibited VEGF-dependent angiogenic response at well tolerated doses. Mice with primary and metastatic tumors treated with Everolimus showed a significant reduction in blood vessel density when compared to controls.

The potential of Everolimus as an anti-cancer agent was shown in rodent models. Everolimus is orally bioavailable, residing longer in tumor tissue than in plasma in a subcutaneous mouse xenograft model, and demonstrating high tumor penetration in a rat pancreatic tumor model. The pharmacokinetic profile of Everolimus indicates sufficient tumor penetration, above that needed to inhibit the proliferation of endothelial cells and tumor cell lines deemed sensitive to Everolimus *in vitro*.

Everolimus administered orally daily was a potent inhibitor of tumor growth, at well tolerated doses, in 11 different mouse xenograft models (including pancreatic, colon, epidermoid, lung and melanoma) and two syngeneic models (rat pancreatic, mouse orthotopic melanoma). These models included tumor lines considered sensitive and “relatively resistant” *in vitro*. In general, Everolimus was better tolerated in mouse xenograft models than standard cytotoxic agents (i.e., doxorubicin and 5-fluorouracil), while possessing similar anti-tumor activity. Additionally, activity in a VEGF-impregnated subcutaneous implant model of angiogenesis and reduced vascularity (vessel density) of Everolimus-treated tumors (murine melanoma) provided evidence of *in vivo* effects of angiogenesis.

It is not clear which molecular determinants predict responsiveness of tumor cells to Everolimus. Molecular analysis has revealed that relative sensitivity to Everolimus *in vitro* correlates with the degree of phosphorylation (activation) of the AKT/PKB protein kinase and the S6 ribosomal protein; in some cases (i.e., glioblastoma) there is also a correlation with PTEN status.

In vivo studies investigating the anti-tumor activity of Everolimus in experimental animal tumor models showed that Everolimus monotherapy typically reduced tumor cell growth rates rather than produced regressions. These effects occurred within the dose range of 2.5 mg to 10 mg/kg, orally once a day.

In preclinical models, the administration of Everolimus is associated with reduction of protein phosphorylation in target proteins downstream of mTOR, notably phosphorylated S6 (p-S6) and p-4E-BP1, and occasionally with an increase in phosphorylated AKT, a protein upstream of mTOR signaling pathway.

All significant adverse events observed in toxicology studies with Everolimus in mice, rats, monkeys and mini-pigs were consistent with its anticipated pharmacological action as an anti-

proliferative and immunosuppressant and at least in part reversible after a 2 or 4-week recovery period with the exception of the changes in male reproductive organs, most notably testes.

In vitro genotoxicity studies covering relevant genotoxicity end-points showed no evidence of clastogenic or mutagenic activity.

In male fertility studies in rats, testicular morphology was affected at 0.5 mg/kg and above, and sperm motility, sperm head count and plasma testosterone levels were diminished at 5 mg/kg which corresponded to 0.7 times the estimated clinical exposure at 10 mg/day, and caused a decrease in male fertility. There was evidence of reversibility. Female fertility was not affected, but everolimus caused an increase of pre-implantation loss in female rats at doses > 0.1 mg/kg, suggesting it could also potentially impact fertility in females. Everolimus crossed the placenta and was toxic to the conceptus. In rats, everolimus caused embryo/fetotoxicity at systemic exposure below the planned therapeutic level comprising mortality and reduced fetal weight. The incidence of skeletal variations and malformations at 0.3 and 0.9 mg/kg (e.g. sternal cleft) was increased. In rabbits, embryo toxicity was evident by an increase in late resorptions. Effects of everolimus on the pre- and postnatal development of rats were limited to slightly affected body weight and survival in the F1-generation at ≥ 0.1 mg/kg, and did not indicate a specific toxic potential.

The potential reproductive risk for humans is unknown. However, due to the observed malformations in rats, everolimus should be considered potentially teratogenic. Everolimus should not be given to pregnant women unless the potential benefit outweighs the potential risk for the fetus. Women of childbearing potential should be advised to use highly effective contraception methods while they are receiving everolimus and up to 8 weeks after treatment has been stopped. It is not known whether everolimus is excreted in human milk. In animal studies, everolimus and/or its metabolites were readily transferred into the milk of lactating rats. Therefore women who are taking everolimus should not breastfeed.

Further details can be found in the Everolimus Investigator's Brochure.

2 Rationale

[name] and colleagues developed a mouse model to study the effects of salivary gland radiation on glandular functions. Analysis of salivary gland cell proliferation and apoptosis in irradiated mice demonstrated that expression of Akt or treatment with IGF-1 protected irradiated salivary glands; the protective effect of IGF-1 was dependent on autophagy, as evidenced by the lack of protection in IGF-1 treated mice in which Atg5 was conditionally deleted in the salivary gland. Subsequently, [name] and colleagues showed that mice irradiated with a single dose of radiation (5Gy) and treated with the mTOR inhibitor CCI-779 for five days (experimental days 4-8) had salivary flow rates and amylase secretion similar to unirradiated controls and statistically increased when compared to irradiated mice (Morgan-Bathke 2014). A follow-up mouse pilot study was conducted with a radiation regimen of 2 Gy/day for 5 consecutive days followed by three injections of CCI-779 at four (experimental days 9-11), fourteen (experimental days 22-24) or 30 days (experimental days 38-40) after the last radiation treatment. Preliminary analysis at 60 days post-radiation suggests that **administration of CCI-779 four or fourteen days after radiation leads to improved salivary output** while administration 30 days later did not produce an improvement.

Impact: Reduction in saliva production and oral dryness can have a devastating effect on oral health that potentially leads to malnutrition and poor quality of life. Common palliative therapies for xerostomia include oral lubricants, saliva substitutes, and saliva stimulants (gum, pilocarpine). Unfortunately, these therapies are short-lived and have not consistently demonstrated the ability to relieve xerostomia symptoms. Therefore these patients are left with very few options and this research could provide a long-term solution for these individuals.

This research project brings together a newly-formed, diverse, interdisciplinary team to solve this complex problem. This team takes advantage of the expertise at both Banner – University Medical Center and St. Joseph's Hospital and Medical Center and the ability to recruit patients in Phoenix and Tucson. It extends the mouse model work conducted by the [name] lab to a phase 0 “proof of principle” clinical trial.

Rapamycin derivatives exhibit considerable similarities in mechanism of action constituting a drug class effect. Therefore, this trial is proposing the use of everolimus due to the ease of administration (orally), which we postulate will have similar biological effects as CCI-779. If successful, the opportunity to expand to a randomized, placebo-controlled, double-blind clinical trial is envisioned.

3 Objectives and endpoints

Initial Objective

Document the safe everolimus dose (5 mg versus 10 mg) to be used in the post radiation or chemoradiation setting for salivary function restoration, using a 3 + 3 design.

Once the safe dose has been defined:

Primary Objective

To describe the recovery of salivary gland function after administration of a 5-day course of everolimus, administered two weeks after completion of radiation or chemoradiation therapy

Primary endpoint

The primary end point of the analysis will be the percent recovery of salivary gland function, with pre-everolimus treatment saliva flow rate as the denominator and the saliva flow rate at 3 months after completion of radiation or chemoradiation therapy as the numerator.

Secondary Objectives

- To describe the decrease of saliva flow rates during radiation or chemoradiation therapy
- To describe the changes in saliva protein composition during radiation or chemoradiation therapy and following administration of a 5-day course of everolimus

Secondary endpoints

Secondary endpoints will be:

- the decrease of saliva flow rates (compared to baseline prior to definitive treatment) during radiotherapy treatment at 3, 6 weeks and prior to everolimus administration and the subsequent recovery of saliva flow rates at completion of the 5 day everolimus course and 1, 3 and 6 months after RT/chemoRT completion to determine the kinetics and stability of saliva flow rate recovery.
- protein composition within the saliva will be measured and will be expressed as percent decrease and recovery of amylase at all available time points.

- Xerostomia Visual Analog Scale survey and Xerostomia Inventory survey will be obtained from each participant at all available time points (See Appendix A and B).

4 Study design

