and if no additional DLT occurs in the expanded cohort, dose escalation to full dose (10 mg po daily) will follow [in this case, total number of patients in the trial: 16; 6 in the 5 mg cohort, 10 in the 10 mg cohort].

-If 2 DLT occur, no escalation to full dose (10 mg po daily) will be attempted, and cohort will

be expanded to 10 patients.) [in this case, total number of patients in the trial: 10; all in the 5 mg cohort].

As a result of these possibilities, total number of patients included in this phase 0, proof of principle trial can range from a minimum of 10 to a maximum of 16 total patients.

Maximum number of 16 patients will occur if a DLT occurs in one of the first 3 patients in the 5 mg cohort, and no DLT occurs in the additional 3 expanded cohort patients (for a total of 6 patients in the 5 mg cohort). Subsequently, 10 additional patients will be enrolled in the 10 mg cohort, for a maximum total of 16 patients.

Procedures:

Stimulated Salivary flow measurements:

Patients will undergo both unstimulated whole saliva collection and stimulated whole saliva collection at each visit. Stimulated whole saliva collection measures the ability of the gland to respond to an external stimulus, which is necessary when eating. It is also likely that this measurement will correlate with swallowing difficulties. The average stimulated saliva output for a normal person is 1.5–2.0 mL/min and some studies have used a \leq 0.5–0.7 mL/min cutoff for hyposalivation determination.

- Patients must fast overnight, however, they may eat 2 hours prior to their scheduled appointment. They are encouraged to perform oral hygiene immediately after eating their meal to remove any remaining food particles, but no later than the two hour time period before their scheduled appointment. They also need to refrain from smoking two hours prior to their scheduled appointment.
- Saliva production is stimulated by the patient chewing unflavored gum base or paraffin wax (1-2g) for 1 minute. The saliva is then collected by the patient spitting into pre-weighed specimen cups during this time frame

Unstimulated Whole Saliva Flow Rate and Collection

- 1) On the day of saliva collection, patient is to not have eaten for 2 hours prior to their scheduled collection appointment
 - a) No enteral feedings for 2 hours prior to collection appointment

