- 9) If the patient is too dry, (dry mouth), it is possible to add the weight of the gum base to the pre-weight measure with the gum base in the cup of saliva.

Analysis of saliva: The collection tubes are weighed before and after saliva collection. The difference equates to the total mL collected which is divided by the number of minutes of collection. Saliva is stored at -80°C for further analysis on salivary protein composition at a later date (described in correlatives below).

The comorbidity of mucositis is an important consideration in this study due to the development of this condition following radiotherapy and as a side effect from chronic use of everolimus. Treatment with everolimus has been designed to begin two weeks after radiotherapy to allow radiation-induced mucositis to start improving. In a pre-clinical model,

concurrent rapamycin treatment with radiotherapy (6Gy/day X 5 days) prevents mucositis due in part to increased expression of mitochondrial superoxide dismutase (MnSOD) (Iglesias-Bartolome 2012). Given the short duration of treatment in this trial (5 days), a delay in the start of everolimus until two weeks after radiotherapy and evidence from this pre-clinical study, we postulate that mucositis will not be a major concern. Patients will be closely monitored for worsening mucositis response once treated with everolimus and if mucositis worsens in 2 out of the first 6 patients, then everolimus 50% dose reduction will be implemented.

5 Population

Patients with locally advanced squamous cell carcinoma of the head and neck, treated with curative intent either in the post-operative or definitive setting with high dose radiotherapy (≥ 50 Gy) with or without chemotherapy will be eligible. Patients will be stratified for exploratory analyses in the analysis phase on the basis of ipsilateral vs bilateral neck irradiation. There will be one treatment group with each patient serving as their own control.

This study will evaluate the response in 10 – 16 patients enrolled at both facilities: St. Joseph's Hospital and Medical Center in Phoenix and Banner – University Medical Center in Tucson (details and justification of sample size in statistical methods) to determine if the proposed everolimus dosing schedule of 5 days is sufficient to show recovery of salivary gland function to pre-treatment levels.

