9.1 Statistical methods

All patients will have their salivary output measured before radiotherapy, 3 weeks after the start of radiotherapy, and at the end of radiotherapy (6 weeks). Patients with clinically severe gland dysfunction (i.e., those with loss of at least 50% of the pre-radiotherapy value) will be eligible for everolimus treatment. Follow-up measurements will be obtained prior to everolimus administration, at completion of the 5 day everolimus course at 1 month, 3 months and 6 months after RT/chemoRT completion.

The primary end point of the analysis will be the percent recovery of salivary gland function, with pre-everolimus treatment saliva flow rate as the denominator and the saliva flow rate at 3 months after completion of radiation or chemoradiation therapy as the numerator.

It is our expectation that because of the short exposure to everolimus (a total of 5 days only), the well described everolimus related toxicities will not develop.

However, following discussions with the company (Novartis), two dose levels will be evaluated: a starting dose of 5 mg po daily, will initially be evaluated in a cohort of 3 patients.

For the purpose of this trial, dose-limiting toxicity (DLT) is defined as an everolimus-related grade 3 or higher AE.

Toxicity will be graded based on the Common Terminology Criteria for Adverse Events (CTCAE) Version 4.03.

(<http://www.hrc.govt.nz/sites/default/files/CTCAE%20manual%20-%20DMCC.pdf>)

As mentioned, we will start treating enrolled patients on the lower dose level.

-If no DLT occurs, will proceed with dose escalation to the full FDA-approved dose (10 mg po daily) [in this case, total number of patients in the trial: 13; 3 in the 5 mg cohort, 10 in the 10 mg cohort].

-If 1 DLT occurs, cohort will be expanded to additional 3 patients; and if another DLT occurs in this expanded cohort, no escalation to full dose (10 mg po daily) will be attempted, and cohort will be expanded to 10 patients [in this case, total number of patients in the trial: 10; all in the 5 mg cohort];

and if no additional DLT occurs in the expanded cohort, dose escalation to full dose (10 mg po daily) will follow [in this case, total number of patients in the trial: 16; 6 in the 5 mg cohort, in the 10 mg cohort].

-If 2 DLT occur, no escalation to full dose (10 mg po daily) will be attempted, and cohort will be expanded to 10 patients.) [in this case, total number of patients in the trial: 10; all in the 5 mg cohort].

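### The primary 'percent recovery' divides by the already reduced pre-everolimus flow, so 100% means no change and the figure cannot show the return to pre-treatment levels that Section 5 aims at

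*Protocol*

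**What the plan says.** The Primary endpoint paragraph of Section 3 names the outcome as "the percent recovery of salivary gland function, with pre-everolimus treatment saliva flow rate as the denominator". Section 9.1 repeats the definition, "with pre-everolimus treatment saliva flow rate as the denominator and the saliva flow rate at 3 months after completion of radiation", so this is not a slip in one place. Section 9.1 plans the mean of this quantity with a 95% confidence interval.

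Only patients with marked loss of function receive everolimus. Section 9.1 describes them as "those with loss of at least 50% of the pre-radiotherapy value".

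Two statements say what the endpoint is for. The primary objective in Section 3 is descriptive: "To describe the recovery of salivary gland function after administration of a 5-day course of everolimus". Section 5 goes further and says the study will determine whether the five-day schedule "is sufficient to show recovery of salivary gland function to pre-treatment levels". It does not define that last phrase.

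One secondary endpoint in Section 3 uses a pre-radiotherapy reference: "the decrease of saliva flow rates (compared to baseline prior to definitive treatment". The reference is attached to the decrease. The later recovery in the same item has no stated reference. Section 9.1 plans only graphical exploration for changes in the secondary endpoints over time.

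**The concern.** A reader who sees a mean percent recovery of 100% will take it that function came back in full. On this scale it means that nothing changed between the pre-everolimus visit and three months. A mean above 100% can look like more than full recovery while patients remain far below their flow before radiotherapy.

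The Section 5 aim is also left without a planned numerical answer. The primary ratio does not contain pre-radiotherapy flow, so it cannot show whether that level was regained. Section 5 goes on to say that the data will guide choices for patients with partial improvement. Calling an improvement partial requires a scale on which full recovery has a fixed value, and this ratio has none.

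**Working it through.** **Inputs.** Let F0 be flow before radiotherapy, Fe flow just before everolimus and F3 flow at three months. All three are collected (Sections 4.1 and 9.1). The share lost is L = 1 − Fe/F0. The primary endpoint is R = 100 × F3/Fe. The only value of L in the protocol is the 50% entry threshold; 75% and 90% below are illustrative.

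**The plan's own figure.** Section 9.1 says ten patients give a standard error of 0.32 of the standard deviation. 1/√10 = 0.316, which agrees. It depends only on the number of patients, so it is the same whichever flow is the denominator.

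**No change.** If F3 = Fe, R = 100%, whatever L is.

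**Full return.** If F3 = F0, R = 100 × F0/Fe = 100/(1−L). In the other direction, F3 as a percentage of F0 is R × (1−L).

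| L | R for full return | Percent of F0 when R = 200% | Percent of F0 if unchanged (R = 100%) |
|---|---|---|---|
| 50% | 200% | 100% | 50% |
| 75% | 400% | 50% | 25% |
| 90% | 1000% | 20% | 10% |

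The same score of 200% is full return in one patient and one fifth of the original flow in another.

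**Effect on the headline mean (assumed data).** Take ten patients with residual flow r = Fe/F0 evenly spaced from 10% to 50%, each gaining 10 points of pre-radiotherapy flow. Then R = 100 × (1 + 0.10/r). The mean is 142.6%, with a t-based 95% interval (9 df) of 124.4 to 160.7, while mean flow moves from 30% to 40% of the original. If the lowest residual is 20% instead, the mean is 131.0% (124.0 to 138.1); if it is 5%, the mean is 158.6% (118.9 to 198.2).

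**The other reading of Section 5.** If pre-treatment meant pre-everolimus, the aim would be met at R = 100%, that is, by a patient with no improvement. That reading does not rescue the sentence. The entry rule and the flow-decrease endpoint both refer to the level before radiotherapy.

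**The case against.** The strongest reply is that the ratio suits what the trial sets out to do. The primary objective only describes recovery after a five-day course, each patient is their own control, and change since the pre-everolimus visit fits both. Numerator and denominator are spelled out twice, and no test or success threshold is tied to 100%. The pre-radiotherapy comparison is partly planned through the secondary endpoint, and no data are lost. All of this stands. It limits the fault to the label and to the conclusion the figure can carry. It does not remove the mismatch with Section 5, because the secondary endpoint gives its reference for the decrease only and is to be explored graphically.

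Three stronger readings are tempting, and the protocol does not support them.

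- *The endpoint is invalid.* It is not. It measures relative change since everolimus correctly.
- *By the protocol's own figures, a 200% score can still be hyposalivation.* Section 4.1 says "The average stimulated saliva output for a normal person is 1.5–2.0 mL/min" and cites a "0.5–0.7 mL/min cutoff for hyposalivation determination". For flow B before radiotherapy and cutoff c, a 200% score stays at or below the cutoff only if 2B(1−L) ≤ c, so L ≥ 1 − c/(2B). With B = 1.5 and c = 0.7 this is 76.7%; with B = 2.0 and c = 0.5 it is 87.5%. The claim therefore needs an assumed normal baseline and an assumed loss of roughly 77–88% or more. At a loss of 50%, a 200% score is full return, 1.5–2.0 mL/min. These figures are also for stimulated flow. Both stimulated and unstimulated saliva are collected, and the endpoint definition does not say which is used.
- *The mean must be replaced by a median or geometric mean.* A mean of ratios can be pulled upward by measurement error, but the size rests on error values the protocol does not give. The choice of summary can be left to an analysis plan.

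**Conclusion.** The point holds as a matter of labelling and of what the headline figure can conclude. That 100% means no change is exact and needs no assumption. Full return scores 100/(1−L), also exact: 200% at the 50% entry threshold and higher for greater loss. Entry appears to be judged at the end of radiotherapy and the denominator is measured about two weeks later, so L at the denominator visit may differ from the entry value. That shifts the score for full return but not the meaning of 100%. The ten-patient figures are illustrations on assumed residual flows and equal absolute gains; they are not predictions.

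The conflict is with the name of the endpoint and with the Section 5 aim, on the sensible reading that pre-treatment means pre-radiotherapy. It is not with the primary objective. The fault should be corrected because it changes how the main result will be read and the correction is cheap. It does not affect the sample size or the 0.32 precision statement.

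**What to change.** 1. In Sections 3 and 9.1, rename the ratio '3-month flow relative to pre-everolimus flow' and state that 100% means no change.
2. Alongside it, report flow as a percentage of pre-radiotherapy flow just before everolimus and at three months, each with a mean and 95% confidence interval. On this scale 100% is full return. Read the Section 5 aim from the three-month value.
3. In Section 5, state that pre-treatment levels means pre-radiotherapy flow.

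The paired difference between the two percentages, and a median or geometric mean for the ratio, are optional additions.

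**Cost.** Wording in three sections and a little more analysis, with no new visits, samples or patients. The headline figure will look smaller. The three-month percentage must be read with the pre-everolimus percentage, because an unchanged patient does not score zero (50% at a loss of 50%). In a single arm, neither measure separates a drug effect from spontaneous change.
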